5.4.3 Exploratory Endpoints

5.4.3.1 Clinical Activity

The major clinical measures of myositis disease activity will include serum creatine kinase normalization, IMACS core set disease activity measures (physician's global activity assessment, patient global activity assessment, muscle strength assessed by MMT, physical function, muscle-associated enzymes, and extramuscular activity assessment), patients' need for new or increased doses of immunosuppressive therapy, changes in patients' immunosuppressive therapy during the follow-up period, photography of skin lesions, and pulmonary function testing. These assessments will be summarized descriptively by treatment group and time point. A descriptive summary of the number and percent of patients who have reached any of the following: 1) complete CK normalization as indicated by relative normalization of 100% and 2) IMACS-defined response will be presented for placebo and each of the MEDI-545 dose group. The major patient-reported outcomes, including SF-36v2 Health Survey, pruritus VAS, CDASI, DLQI, and WPAI: SHP questionnaire will also be summarized descriptively.

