3.1.1 Inclusion Criteria

Patients must meet *all* of the following criteria:

1. Male or female adults at least 18 years of age at the time of randomization;
2. Written informed consent obtained from the patient or the patient's legal representative prior to receipt of any study medication or beginning study procedures;
3. Probable or definite PM or DM according to the Bohan and Peter criteria (Bohan, 1975);
4. For patients with PM, documentation of a muscle biopsy result that is consistent with the diagnosis of PM;
5. All patients including those with DM must meet at least two of the following criteria:
 - a. Strength in MMT $\geq 80/150$ but $\leq 125/150$ using the MMT-8 muscle group testing (see Appendix A);
 - b. Patient Global Activity Assessment by visual analog scale (VAS) ≥ 2.0 cm on a 10-cm scale, which is included as part of CLINHAQ (see Appendix B);
 - c. Physician Global Activity Assessment by VAS ≥ 2.0 cm on a 10 cm scale, which is included as part of MDAAT (see Appendix C);
 - d. CLINHAQ (see Appendix B) disability index ≥ 0.25 ;
 - e. Global extramuscular activity assessment ≥ 1.0 cm on a 10-cm VAS scale (this measure is the physician's composite evaluation and is based on assessments of activity scores on the constitutional, cutaneous, skeletal, gastrointestinal, pulmonary and cardiovascular scales of the MDAAT [Appendix C]);
6. Subjects with PM must have an elevation of serum CK or aldolase at a minimum level of $1.3 \times$ upper limit of normal (ULN) or serum CK or aldolase at least 2-fold higher than the patient's own lowest value since diagnosis;
7. Subjects with DM must have either an elevated CK or aldolase as above (per inclusion criterion #6) or other laboratory evidence of active myositis. This could include either abnormal signal on skeletal muscle MRI suggestive of inflammation or an electromyogram demonstrated muscle membrane irritability (e.g., fibrillation potentials, positive sharp waves, complex repetitive discharges) and short duration, small amplitude, polyphasic motor unit action potentials.
8. Patients randomized to Dose Cohorts 1, 2, 3A, and 4 must have median fold overexpression of the top 25 type I IFN-inducible genes of 4-fold or greater in whole blood or muscle at the time of screening; patients randomized to Dose Cohort 3B must have low/undetectable expression of type I IFN-inducible genes;

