3.6.6 Evaluations of Disease Activity

3.6.6.1 Serum Creatine Kinase Normalization

Creatine kinase has been the most useful serum enzyme for the diagnosis and assessment of adult patients with DM or PM. It is the most sensitive enzyme to muscle injury, is at times the only one elevated, and the degree of serum CK elevation is often greater than that seen with other muscle enzymes. As emphasized by Bohan and Peter (Bohan, 1975), trends in serum activity but not single values accurately reflect disease activity in individuals and are useful in the management of these patients. In fact, the trend of the CK has been frequently used in clinical practice to assess response to therapy and is reported in case studies to support evidence of clinical improvement. Preliminary data from MedImmune researchers suggest a correlation between CK values and level of type I IFN gene signature in peripheral blood.

Serum CK will be measured as described in Table 4 and Table 5. The relative normalization of serum CK will be derived from the serum CK ULN and the serum CK levels at baseline (Study Day 0 predose) and at the current visit (eg, Study Day 84) using the following formula:

$$\text{Relative Serum CK Normalization} = \frac{\text{Serum CK on Study Day 0} - \text{Serum CK on Current Visit}}{\text{Serum CK on Study Day 0} - \text{Serum CK ULN}} \times 100\%$$

For example, if the serum CK is 1000 U/L on Study Day 0 and the serum CK on the Current Visit is 500 U/L, then the relative serum CK normalization is 62.5% based on a serum CK ULN of 200 U/L.

$$\frac{1000 \text{ U/L} - 500 \text{ U/L}}{1000 \text{ U/L} - 200 \text{ U/L}} \times 100\% = 62.5\%$$

However, if the serum CK on the Current Visit is less than the serum CK ULN, the relative CK normalization will be 100%.

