5 STATISTICAL CONSIDERATIONS

5.1 General Considerations

All data will be provided in data listings sorted by treatment group and patient number. All tabular summaries will be presented by treatment group. Categorical data will be summarized by the number and percentage of patients in each category. Continuous variables will be summarized by descriptive statistics including mean, standard deviation, median, minimum, and maximum. No formal statistical tests are planned. Missing data will be treated as missing. No data will be imputed unless otherwise specified. Study Baseline values will be defined as the last valid assessment prior to the first administration of study drug. All data will be collected from screening through Study Day 350.

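### Complete CK normalization rests on one unconfirmed value below ULN with no minimum Day 0 CK, so patients who start near ULN can be counted through noise

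*Protocol*

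**What the plan says.** Section 3.6.6.1 defines relative CK normalization as the fall from Day 0 divided by the distance from Day 0 CK to ULN. It then adds a cap: "if the serum CK on the Current Visit is less than the serum CK ULN, the relative CK normalization will be 100" percent. Section 5.4.3.1 names two responder counts. One is the IMACS-defined response; the other is "complete CK normalization as indicated by relative normalization of 100" percent. The count covers patients who have reached that state. No repeat value, duration, visit or minimum starting CK is given.

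In introducing the measure, Section 3.6.6.1 says that "trends in serum activity but not single values accurately reflect disease activity in individuals".

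Section 3.1.1 does not guarantee a raised CK at entry:
- Polymyositis (PM), criterion 6: "Subjects with PM must have an elevation of serum CK or aldolase at a minimum level of" 1.3 times ULN. Aldolase alone can satisfy this.
- PM, alternative route: "serum CK or aldolase at least 2-fold higher than the patient's own lowest value since diagnosis". This has no floor relative to ULN.
- Dermatomyositis (DM), criterion 7: raised enzymes as above "or other laboratory evidence of active myositis", which may be MRI or EMG findings.

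The reference value is itself a single measurement. Section 5.1 states: "Study Baseline values will be defined as the last valid assessment prior to the first administration of study drug".

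**The concern.** The entry and normalization thresholds nearly touch. A patient who enters exactly at 1.3 times ULN needs a 23% fall at one visit to score 100%. One who enters through aldolase or the 2-fold rule with CK at 1.1 times ULN needs 9%. Changes of that size can arise from assay and biological variation alone. A patient whose Day 0 CK is already below ULN needs no fall at all.

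The rule also departs from the protocol's own argument, which prefers trends to single values and then builds a status on a single value.

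At stake is the reading of one of only two named responder counts. With six patients on active drug in a cohort, one spurious case moves the proportion by 1/6, about 17 percentage points. No formal tests are planned (Section 5.1), so raw counts will be read directly. Section 3.3 says the interim assessments of clinical activity serve development decisions.

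**Working it through.** **Inputs from the protocol.** The formula, cap and worked example are in Section 3.6.6.1, and the entry levels in Section 3.1.1. Table 4 gives seven post-baseline CK draws through Day 98 (Days 14, 28, 42, 56, 70, 84, 98).

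**Inputs not in the protocol.** The within-patient CV is assumed and run from 10% to 40%. CK is taken as log-normal around a constant true level of m × ULN, with independent visits and no treatment effect.

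**1. The protocol's own figure.** Baseline 1000, current 500, ULN 200: (1000 − 500)/(1000 − 200) = 62.5%, as stated.

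**2. The same rule near the cut-off (ULN 200).**
- Baseline 260 (1.3 × ULN), current 199: the cap gives 100%. The fall needed is 1 − 1/1.3 = 23.1%. A halving from 1000 to 500 scores less.
- Baseline 1.1 × ULN: the fall needed is 1 − 1/1.1 = 9.1%.
- Baseline 180, current 190: the cap gives 100% although CK rose.
- Baseline 180, current 250: (180 − 250)/(180 − 200) = 350%, a rise scored as improvement. At baseline = ULN the denominator is zero.

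**3. Chance of a value below ULN with no true change.** Let s = √ln(1 + CV²). Then:
- one visit: p = Φ(−ln m / s)
- at least one of 7 visits: 1 − (1 − p)⁷
- two consecutive values somewhere in 7 visits: start with a = 1, b = c = 0 and apply seven times a′ = (a + b)(1 − p), b′ = a·p, c′ = c + b·p; the answer is c
- Days 84 and 98 both below ULN: p²

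Example, m = 1.3 and CV 20%: s = √ln 1.04 = 0.198; p = Φ(−0.262/0.198) = 9.3%; 1 − 0.907⁷ = 49%.

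Results for m = 1.3:

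| CV | One visit | Any of 7 | Two consecutive in 7 | Days 84 and 98 |
|---|---|---|---|---|
| 10% | 0.4% | 2.9% | 0.0% | <0.1% |
| 15% | 3.9% | 24.5% | 0.9% | 0.2% |
| 20% | 9.3% | 49.4% | 4.7% | 0.9% |
| 30% | 18.6% | 76.3% | 17.0% | 3.4% |
| 40% | 24.8% | 86.4% | 27.8% | 6.1% |

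**4. Higher baselines.** The any-of-7 chance falls quickly:
- m = 1.5: 13.4% at CV 20%, 45.7% at CV 30%
- m = 2: 0.2% at CV 20%, 6.2% at CV 30%, 22.6% at CV 40%
- m = 5: 0.0% at every CV in the range

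The problem is confined to patients who start near ULN. The protocol gives no distribution of baseline CK, so it does not support a cohort-wide rate.

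**The case against.** The strongest reply concerns size and reading, and much of it stands.

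- **Ever reached or per visit.** The sentence before the responder count in Section 5.4.3.1 says the activity measures are summarized by time point. If that governs the count, only the one-visit column applies. The wording allows either reading, which is why the plan should say.
- **Assumed CV.** At CV 10% even the worst case is about 3%. A reader might infer that patients near the cut-off will routinely be counted as normalized, or that half or more of a cohort could be. The documents support neither: the large figures describe one patient exactly at 1.3 times ULN, with CV of at least 20%, under an ever-reached count.
- **Group size.** Cohorts may expand by four patients (Section 2.4.1), and Section 1.5 reports 51 already dosed, an average of 51/5 ≈ 10 per cohort. The 17-point step is for the planned six active patients; with more, it is smaller.
- **No built-in direction.** A reader might infer a bias towards the drug. Blinded placebo patients carry the same noise, so the expected effect is to raise and blur every group. Chance imbalance in low baselines between small groups could still mimic or hide a dose trend.
- **Limited role.** The count is exploratory, and dose escalation (Section 4.9) rests on safety. The protocol says normalization, not response, and a CK below ULN is literally normal.
- **Left to the analysis plan.** A confirmation rule could be added there. But the 100% cap without a baseline condition is fixed in the protocol, as is its conflict with the warning about single values.

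**Conclusion.** The point holds in a limited form. The protocol counts complete CK normalization from one value below ULN, without confirmation or a minimum Day 0 CK. That sits badly with its own statement about single values and with entry routes that admit patients at or below 1.3 times ULN.

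Patients who start near ULN can therefore be counted through noise, and those already below ULN without any fall. For a true CK of 1.3 times ULN the chance is about 0.4–25% at one visit and 3–86% at any of seven visits, across an assumed CV of 10–40%. The upper figures depend on that CV, on independent visits and on an ever-reached count. At 2 times ULN with CV 20% the effect is negligible.

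The primary safety objective is untouched. This is an inexpensive improvement to an exploratory summary; it does not invalidate the trial.

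**What to change.** In Sections 3.6.6.1 and 5.4.3.1:

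1. Restrict the complete CK normalization count to patients whose Day 0 CK is elevated (above ULN, or at least 1.3 times ULN; choose one and state it), and report that denominator. This also removes the cases where the formula is undefined or has the wrong sign.
2. State whether the count is per visit or ever reached.
3. Make the headline count normalization confirmed at two consecutive scheduled visits. For the placebo-controlled period, use Days 84 and 98.
4. Show the single-value count alongside, for continuity with earlier interim looks.

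**Cost.** No new samples: CK is already drawn at every dosing visit and at the follow-up visits from Day 196. The denominator shrinks. A patient who first normalizes at the last visit of a period, or misses the confirming visit, appears only in the single-value count. Confirmation reduces false counts but does not abolish them: at 1.3 times ULN and CV 40%, about 6% remain on the Day 84 and 98 rule. Positive correlation between neighbouring visits would raise that figure.

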5.4.3.2 Biological Activity and Mechanism of Action

Type I IFN-inducible genes will be used to measure the pharmacodynamics of MEDI-545. Whole blood samples and muscle and skin biopsies will be used to analyze the effects of MEDI-545 on levels of mRNA for type I IFN-inducible genes, using microarray analyses. PCR assay on selected panel of genes may be used to confirm the microarray results.

Other descriptive analyses may include levels of expression of type I IFN-inducible proteins and non-type I IFN-inducible genes in whole blood and muscle and skin biopsies, IHC of muscle and skin biopsies, serum IFN- α levels, proteomics and changes in autoantibody levels or profiles, flow cytometry results, and gene polymorphisms associated with response to MEDI-545.

5.5 Interim Analyses

Interim analysis of the type I inducible gene expression will be performed after all patients in each dose cohort complete Study Day 28 evaluations.

Interim analyses on the safety and efficacy endpoints will be performed at the following time points in the study:

- After the first 2 cohorts complete the Study Day 98 evaluation;
- When at least 8 patients in Dose Cohort 4 complete the Study Day 98 evaluation; and
- After all cohorts complete Study Day 196 evaluation.

6 DATA COLLECTION AND MONITORING

The primary source document for this study will be the patient's medical record. If separate research records are maintained by the investigator(s), both the medical records and the research records will be considered the source documents for the purposes of auditing the study.

Data recorded on source documents will be transcribed onto a validated data collection method provided by MedImmune or designee. Collected data will be reviewed by the sponsor or designee, with a copy retained by the investigator.

The study will be monitored by MedImmune or its designee on a regular basis throughout the study period. All study documents (patient files, signed informed consent forms, copies of eCRFs, Study File Notebook, etc.) must be kept secured for a period of 2 years following marketing of MEDI-545 or for 2 years after centers have been notified that the IND has been discontinued. There may be other circumstances for which MedImmune is required to maintain study records and, therefore, MedImmune should be contacted prior to removing study records for any reason.

7 HUMAN SUBJECTS

7.1 Ethics and Regulatory Considerations

The study will be conducted according to the Declaration of Helsinki, Protection of Human Volunteers (21 CFR 50), Institutional Review Boards (21 CFR 56), and Obligations of Clinical Investigators (21 CFR 312).

The protocol will be reviewed and approved by the Institutional Review Board (IRB) or Independent Ethics Committee (IEC) of each participating center prior to study initiation. Serious adverse events regardless of causality will be reported to the sponsor and to the IRB/IEC, and the investigator will keep the IRB/IEC informed as to the progress of the study.

The investigator will explain the nature of the study and will inform the patient that participation is voluntary and that they can withdraw at any time. Written informed consent will be obtained from each patient prior to entry into the study. A copy of the signed consent form will be given to every participant and the original will be maintained with the patient's records.

To maintain confidentiality, all laboratory specimens, evaluation forms, reports and other records will be identified by a coded number and initials only. All study records will be kept in a locked file cabinet and code sheets linking a patient's name to a patient identification number will be stored separately in another locked file cabinet. Clinical information will not be released without written permission of the patient, except as necessary for monitoring by the FDA or the sponsor of the clinical trial. The principal investigator must also comply with all applicable privacy regulations (eg, Health Insurance Portability and Accountability Act of 1996, EU Data Protection Directive 95/46/EC).

7.2 Institutional Review Board (IRB) or Independent Ethics Committee (IEC)

A list of IRB/IEC members should be obtained by the investigator and provided to the sponsor. Any documents that the IRB/IEC may need to fulfil its responsibilities, such as protocol amendments, and information concerning patient recruitment, payment or compensation procedures, or information from the sponsor will be submitted to the IRB/IEC. The IRB/IEC's written unconditional approval of the study protocol and the informed consent form will be in the possession of the investigator and the sponsor before the study is initiated. The IRB/IEC's unconditional approval statement will be transmitted by the investigator to the sponsor prior to shipment of study drug supplies to the site. This approval must refer to the study by exact protocol title and number, and should identify the documents reviewed and the date of review.

Protocol modifications or changes may not be initiated without prior written IRB/IEC approval except when necessary to eliminate immediate hazards to the patients or when the change(s) involves only logistical or administrative aspects of the study. Such modifications will be submitted to the IRB/IEC and written verification that the modification was submitted should be obtained.

The IRB/IEC must be informed by the principal investigator of informed consent changes or revisions of other documents originally submitted for review; serious and/or unexpected adverse

experiences occurring during the study; new information that may affect adversely the safety of the patients or the conduct of the study; an annual update and/or request for re-approval; and when the study has been completed.

7.3 Informed Consent

The principles of informed consent in the current edition of the Declaration of Helsinki should be implemented before any protocol-specified procedures or interventions are carried out. Informed consent will be obtained in accordance with 21 CFR 50.25.

Information should be given in both oral and written form, and patients or their legal representatives must be given ample opportunity to inquire about details of the study. The written consent document will embody the elements of informed consent as described in the Declaration of Helsinki and will also comply with local regulations.

Patients must be informed about the aims, expected benefits, possible risks (including a statement that the particular treatment or procedure may involve risks to the patient or the fetus, if the patient should become pregnant) which are currently unforeseeable. They must also be informed of alternative procedures. Patients must receive an explanation as to whether any compensation and any medical treatments are available if injury occurs and, if so, what they consist of, or where further information may be obtained. They must be informed whom to contact for answers to any questions relating to the research project. The patients must be informed that participation is voluntary and that they are free to withdraw from the study for any reason at any time, without penalty or loss of benefits to which they are otherwise entitled. The extent of the confidentiality of patient records must be defined, and patients must be informed that applicable data protection legislation will be complied with. Patients must be informed that the monitor(s), auditor(s), IRB/IEC members, and the regulatory authorities will be granted direct access to the patient's original medical records for verification of clinical trial procedures and/or data, without violating the confidentiality of the patient, to the extent permitted by the applicable laws and regulations and that, by signing a written informed consent form, the patient or the patient's legally acceptable representative is authorizing such access.

The consent form generated by the investigator must be approved by the IRB/IEC and be acceptable to MedImmune. Consent forms must be written so as to be understood by the prospective patient. Informed consent will be documented by the use of a written consent form approved by the IRB/IEC and signed and dated by the patient or the patient's legally authorized representative, and by the person who conducted the informed consent discussion. The signature confirms the consent is based on information that has been understood. Each patient's signed informed consent form must be kept on file by the investigator for possible inspection by Regulatory Authorities and/or MedImmune professional and Regulatory Compliance persons. The patient or the patient's legally acceptable representative should receive a copy of the signed and dated written informed consent form and any other written information provided to the patients, and should receive copies of any signed and dated consent form updates and any amendments to the written information provided to patients.

8 STUDY COMPLETION

All materials or supplies provided by the sponsor will be returned to the sponsor upon study completion. The investigator will notify the IRB/IEC when the study has been completed.

9 PUBLICATIONS

Publication by the site of any data from this study must be carried out in accordance with the clinical study agreement.

10 CHANGES IN THE PROTOCOL

The protocol may not be modified without written approval of the sponsor. All changes to the protocol must be submitted to the FDA and IRB/IEC, and must be approved by the IRB/IEC prior to their implementation. Documentation of IRB/IEC approval must be sent to the sponsor immediately upon receipt.

Summary of Changes from Version 1.0 to Version 2.0 of the Study Protocol

Version 1.0 of the protocol () was amended to Version 2.0 (dated) to provide more information about genetic testing; to include pregnancy testing before each dose of MEDI-545 and every 12 weeks thereafter; to exclude patients with a history of active tuberculosis; to clarify that Quantiferon-TB Gold assay for the diagnosis of latent tuberculous infection will be done at selected sites; to clarify that IVIG may be given in the study; to clarify other events requiring immediate reporting, and to correct typographical errors. The changes made to Version 1.0 of the protocol to create Version 2.0 are summarized in Appendix J.

Summary of Changes from Version 2.0 to Version 3.0 of the Study Protocol

Version 2.0 of the protocol (dated) was amended to Version 3.0 (dated). The major changes include reducing the starting dose of MEDI-545 from 1.0 to 0.3 mg/kg, reducing the highest dose of MEDI-545 from 30.0 to 20.0 mg/kg, and setting the infusion volume at 100 mL and the infusion time to 60 minutes. Other changes include updating the safety information on MEDI-545 and clarification of text. The changes made to Version 2.0 of the protocol to create Version 3.0 are summarized in Appendix J.

Summary of Changes from Version 3.0 to Version 4.0 of the Study Protocol

Version 3.0 of the protocol (dated) was amended to Version 4.0 (dated). The major changes include updating preclinical and clinical information; identification of specific safety biomarkers to analyze infusion reactions; addition of medically significant infusion reactions as an immediately reported event; and clarification of text. The changes made to Version 3.0 of the protocol to create Version 4.0 are summarized in Appendix J.

Summary of Changes from Version 4.0 to Version 5.0 of the Study Protocol

Version 4.0 of the protocol (dated) was amended to Version 5.0 (dated). The major changes include changing the medical monitor; updating preclinical

and clinical information; reducing the highest dose of MEDI-545 from 20.0 to 10.0 mg/kg; reducing the number of patients from 40 to 32; reducing the number of dose cohorts from five to four; indicating that CRPS will no longer be blinded to the study, although they will continue to be part of the project team, revisions to the inclusion and exclusion criteria; provided more detailed information regarding anaphylactic infusion reactions and suggested treatment procedures to the investigators, if any occur. Other revisions include changes to the statistical considerations section and clarification of text throughout the protocol. Finally, a new Table (number 3) was added and the rest of the tables were renumbered. The changes made to Version 4.0 of the protocol to create Version 5.0 are summarized in Appendix J.

Summary of Changes from Version 5.0 to Version 6.0 of the Study Protocol

Version 5.0 of the protocol (dated [REDACTED]) was amended to Version 6.0 (dated [REDACTED]). The major changes include changing the medical monitor; updating preclinical and clinical information; moving the optional DNA analysis from Study Day 0 to Study Day 14; increasing the number of dose cohorts from 4 to 5 by adding Dose Cohort 3B, which will only include patients with low/undetectable gene signature; increasing the number of patients from 32 to 40; providing clarification that a physician must be present at the sites during all study drug administrations; providing clarification that any study drug remaining in the tubing must be flushed with 10 mL to 20 mL normal saline to complete study drug administration; clarifying that patients will provide the vaginal self-collected swabs and clarification that these may also be collected by qualified medical personnel, if approved by the sponsor; providing clarification that patients who become pregnant during the study period must not receive additional doses of study product and should proceed to the follow-up phase beginning at Study Day 185. Other revisions include changes to the statistical considerations section and clarification of text throughout the protocol. The changes made to Version 5.0 of the protocol to create Version 6.0 are summarized in Appendix J.

Summary of Changes from Version 6.0 to Version 7.0 of the Study Protocol

Version 6.0 of the protocol (dated [REDACTED]) was amended to Version 7.0 (dated [REDACTED]). The major changes include: updating the clinical experience with MEDI-545; including the option for patients to enter the long-term study MI-CP212; adding toxicity management guidelines for blood chemistry abnormalities; clarifying medical monitor and Safety Monitoring Committee responsibilities; including 2 additional conditions in which dosing should be discontinued; clarifying the circumstance of patient death as it applies to interruption of study dosing and randomization (ie, death of any subject which, in the opinion of the sponsor, contraindicates further dosing); changing the second interim analysis (which was to occur after all patients in Dose Cohort 4 completed Day 98) to when a minimum of 8 patients in Dose Cohort 4 complete Study Day 98; clarifying that complete clinical response and remission will not be assessed in this study (as the study duration is not long enough to do so); and providing guidance in Appendix J for the management of abnormal LFTs. Some of these changes occur in multiple places in the protocol, including the Study Abstract, when applicable. Changes to the protocol are described in Appendix K.

